9.3. Patient Withdrawal Criteria

Patients may withdraw from participation in the study at any time. The Investigator may withdraw a patient at any time if they believe the safety of the patient or the integrity of the data are at risk. In addition, patients should be withdrawn if they:

- Experience a serious or intolerable AE
- Develop a clinically significant laboratory or ECG abnormality
- Develop proteinuria of 1-2+ or UACR > 30 mg/g as confirmed by a repeat lab test
- Develop eGFR levels < 60 mL/minute/1.73 m² as confirmed by a repeat lab test
- Develop *symptomatic* ALT or AST elevation ≥ 2 x the ULN on two repeat lab tests or develop *asymptomatic* ALT or AST elevation ≥ 3 x the ULN as confirmed by a repeat lab test
- Develop total bilirubin ≥ 2 x the ULN as confirmed by a repeat lab test
- Exhibit suicidal behavior as determined by an affirmative answer on items 4 or 5 on the C-SSRS
- Do not follow guidelines specified in the protocol (i.e., is noncompliant with protocol procedures or Study Medication administration) or specific instructions by the study staff
- Any medically appropriate reason or significant protocol violation, in the opinion of the Investigator
- Are lost to follow up

In case of two consecutive missed safety assessments due to the COVID-19 pandemic, continued patient participation in the study must be discussed by the Investigator and the Medical Monitor.

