13.4.6. Columbia Suicide Severity Rating Scale

The C-SSRS data will be summarized descriptively. Only the following specific suicidal ideation and behavior category questions with any “Yes” responses will be summarized in a frequency distribution table at each post-randomization visit:

- Any Suicidal Ideation Category:
 - Wish to be Dead
 - Non-Specific Active Suicidal Thoughts
 - Active Suicidal Ideation with Any Methods (Not Plan) without Intent to Act
 - Active Suicidal Ideation with Some Intent to Act, without Specific Plan
 - Active Suicidal Ideation with Specific Plan and Intent
- Any Suicidal Behavior Category:
 - Completed Suicide
 - Non-Fatal Suicide Attempt
 - Interrupted Attempt
 - Aborted Attempt
 - Preparatory Acts or Behavior

- Any Suicidal Ideation or Behavior Category

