Definitions of behavioral suicidal events in this scale are based on those used in The Columbia Suicide History Form, developed by [name] and [name], Conte Center for the Neuroscience of Mental Disorders (CCNMD), New York State Psychiatric Institute, [name]. (Oquendo M. A., Halberstam B. & Mann J. J., Risk factors for suicidal behavior: utility and limitations of research instruments. In M.B. First [Ed.] Standardized Evaluation in Clinical Practice, pp. 103 -130, 2003.)

For reprints of the C-SSRS contact [name]., New York State Psychiatric Institute, [name]; inquiries and training requirements contact [contact]

© 2008 The Research Foundation for Mental Hygiene, Inc.

SUICIDAL IDEATION				

Ask questions 1 and 2. If both are negative, proceed to "Suicidal Behavior" section. If the answer to question 2 is "yes", ask questions 3, 4 and 5. If the answer to question 1 and/or 2 is "yes", complete "Intensity of Ideation" section below.
 
1. Wish to be Dead Subject endorses thoughts about a wish to be dead or not alive anymore, or wish to fall asleep and not wake up Have you wished you were dead or wished you could go to sleep and not wake up?
 
If yes, describe:
		Since Last Visit Yes No  		

2. Non-Specific Active Suicidal Thoughts General, non-specific thoughts of wanting to end one's life/commit suicide (e.g., "I've thought about killing myself") without thoughts of ways to kill oneself/associated methods, intent, or plan during the assessment period Have you actually had any thoughts of killing yourself?
 
If yes, describe:
		Yes No  		

3. Active Suicidal Ideation with Any Methods (Not Plan) without Intent to Act Subject endorses thoughts of suicide and has thought of at least one method during the assessment period. This is different than a specific plan with time, place or method details worked out (e.g., thought of method to kill self but not a specific plan). Includes person who would say, "I thought about taking an overdose but I never made a specific plan as to when, where or how I would actually do it...and I would never go through with it." Have you been thinking about how you might do this?
 
If yes, describe:
		Yes No  		

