
4. Active Suicidal Ideation with Some Intent to Act, without Specific Plan Active suicidal thoughts of killing oneself and subject reports having some intent to act on such thoughts, as opposed to "I have the thoughts but I definitely will not do anything about them." Have you had these thoughts and had some intention of acting on them?
 
If yes, describe:
		Yes No  		

5. Active Suicidal Ideation with Specific Plan and Intent Thoughts of killing oneself with details of plan fully or partially worked out and subject has some intent to carry it out Have you started to work out or worked out the details of how to kill yourself? Do you intend to carry out this plan?
 
If yes, describe:
		Yes No  		
INTENSITY OF IDEATION				

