SUICIDAL BEHAVIOR (Check all that apply, so long as these are separate events; must ask about all types)		Since Last Visit
Actual Attempt: A potentially self-injurious act committed with at least some wish to die, as a result of act. Behavior was in part thought of as method to kill oneself Intent does not have to be 100%. If there is any intent/desire to die associated with the act, then it can be considered an actual suicide attempt There does not have to be any injury or harm , just the potential for injury or harm If person pulls trigger while gun is in mouth but gun is broken so no injury results, this is considered an attempt Inferring Intent: Even if an individual denies intent/wish to die, it may be inferred clinically from the behavior or circumstances For example, a highly lethal act that is clearly not an accident so no other intent but suicide can be inferred (e.g., gunshot to head, jumping from window of a high floor/story) Also, if someone denies intent to die, but they thought that what they did could be lethal, intent may be inferred Have you made a suicide attempt? Have you done anything to harm yourself? Have you done anything dangerous where you could have died? 
 What did you do? Did you _____ as a way to end your life? Did you want to die (even a little) when you _____? Were you trying to end your life when you _____? Or did you think it was possible you could have died from _____? 
Or did you do it purely for other reasons / without ANY intention of killing yourself (like to relieve stress, feel better, get sympathy, or get something else to happen)? (Self-Injurious Behavior without suicidal intent)
 
If yes, describe:
		
Total # of Attempts _____		

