Has subject engaged in Non-Suicidal Self-Injurious Behavior? Interrupted Attempt: When the person is interrupted (by an outside circumstance) from starting the potentially self-injurious act (if not for that, actual attempt would have occurred). Overdose: Person has pills in hand but is stopped from ingesting Once they ingest any pills, this becomes an attempt rather than an interrupted attempt Shooting: Person has gun pointed toward self, gun is taken away by someone else, or is somehow prevented from pulling trigger Once they pull the trigger, even if the gun fails to fire, it is an attempt Jumping: Person is poised to jump, is grabbed and taken down from ledge Hanging: Person has noose around neck but has not yet started to hang - is stopped from doing so Has there been a time when you started to do something to end your life but someone or something stopped you before you actually did anything? If yes, describe:		
Yes No □ □		
Aborted Attempt: When person begins to take steps toward making a suicide attempt, but stops themselves before they actually have engaged in any self-destructive behavior Examples are similar to interrupted attempts, except that the individual stops him/herself, instead of being stopped by something else Has there been a time when you started to do something to try to end your life but you stopped yourself before you actually did anything? If yes, describe:		
Yes No □ □		
Preparatory Acts or Behavior: Acts or preparation towards imminently making a suicide attempt This can include anything beyond a verbalization or thought, such as assembling a specific method (e.g., buying pills, purchasing a gun) or preparing for one's death by suicide (e.g., giving things away, writing a suicide note) Has you taken any steps towards making a suicide attempt or preparing to kill yourself (such as collecting pills, getting a gun, giving valuables away or writing a suicide note)? If yes, describe:		
Yes No □ □		
Suicidal Behavior: Suicidal behavior was present during the assessment period?		
Yes No □ □		
Suicide:		
Most Lethal Attempt Date: _____		
Answer for Actual Attempts Only		

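### The C-SSRS withdrawal rule is labelled suicidal behavior but tests only two ideation items, so a recorded attempt or preparatory act does not by itself meet it

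*Protocol*

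**What the plan says.** Protocol Section 9.3 lists the circumstances in which a patient should be withdrawn. The suicidality entry reads "Exhibit suicidal behavior as determined by an affirmative answer on items 4 or 5 on the C-SSRS". The Amendment 2 summary of changes records that FDA requested this criterion; it does not reproduce the request.

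During treatment the C-SSRS is given in its Since Last Visit version (Section 8.2.2; form in Appendix K) at Weeks 2, 4, 6, 8, 10 and 12. On that form:

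- The only numbered questions are the five ideation items. Item 4 is titled "Active Suicidal Ideation with Some Intent to Act, without Specific Plan"; item 5 is active ideation with a specific plan and intent.
- The ideation block opens with a skip instruction: "Ask questions 1 and 2. If both are negative, proceed to" the behavior section. Items 3 to 5 are asked only after a yes on item 2.
- Behavior has its own block, headed "SUICIDAL BEHAVIOR (Check all that apply, so long as these are separate events; must ask about all types". It covers actual, interrupted and aborted attempts and preparatory acts, and closes with a yes/no question on whether "Suicidal behavior was present during the assessment period".

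Protocol Section 13.4.6 and SAP Section 5.5.2 keep the same division. They list the content of items 4 and 5 under ideation, and attempts and preparatory acts under "Any Suicidal Behavior Category".

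**The concern.** The words "Exhibit suicidal behavior as determined by an affirmative answer on items 4 or 5 on the C-SSRS" make items 4 and 5 the test, and that test does not measure what the label says. A site applying the rule literally would find that an aborted attempt or a preparatory act, recorded on the form as suicidal behavior, does not trigger it if items 4 and 5 are negative or were never asked.

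This is a patient-safety rule for the treatment period. If such an event is also not judged a serious or intolerable adverse event, withdrawal rests on the investigator's opinion and not on the criterion written for suicidality. The result is an odd order: ideation with some intent is a named trigger, while an act towards suicide may be left to discretion.

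The primary analysis and the C-SSRS summaries are not at issue.

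**Working it through.** The plan states no figure for this point, so the check is mainly a comparison of texts, followed by a count and a small cost illustration.

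**1. Does the rule's test match its label?** The rule is met if and only if item 4 or item 5 is yes. Applied to the Appendix K form:

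| Form entries | Rule in 9.3 | Behavior recorded? |
|---|---|---|
| Items 1 and 2 no; items 3 to 5 not asked; no behavior | Not met | No |
| Items 1 and 2 no; items 3 to 5 not asked; an attempt or preparatory act marked yes | Not met | **Yes** |
| Item 4 yes; no behavior | Met | No |
| Item 4 or 5 yes; behavior marked yes | Met | Yes |

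The second row is a miss and the third is a mismatch in the other direction. The third is protective, because it acts on intent before any act, and should be kept. Only the second needs repair.

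**2. Can the second row occur?** There are two ways.

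- *Skip pattern.* With items 1 and 2 negative, the rater goes directly to the behavior block, where every type must still be asked about. With item 1 yes and item 2 no, items 3 to 5 are likewise not asked.
- *Denied intent.* For an actual attempt the form says: "Even if an individual denies intent/wish to die, it may be inferred clinically from the behavior or circumstances". An attempt can therefore be recorded for a patient who denies intent.

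Preparatory acts have their own yes/no box ("Preparatory Acts or Behavior: Acts or preparation towards imminently making a suicide attempt"), independent of items 4 and 5.

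**3. Coverage, counted from Section 13.4.6.**

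- Ideation categories: 5, of which the rule names 2 (items 4 and 5).
- Non-fatal behavior categories: 4 (non-fatal attempt, interrupted attempt, aborted attempt, preparatory acts), of which the rule names 0. Completed suicide is left out because withdrawal is then moot.
- Visits after Day 1 at which behavior is already asked: Weeks 2, 4, 6, 8, 10 and 12, which is 6. Week 12 ends treatment, so withdrawal can change management at 6 − 1 = 5 of them.

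**4. Cost of a few more withdrawals.** Inputs from Protocol Section 13.1 and SAP Section 5.1.1: difference 5.2, SD 10, two-sided t-test at 0.05, 60 completers per arm. Power comes from the noncentral t distribution with n₁ + n₂ − 2 degrees of freedom and noncentrality 5.2 / (10 × √(1/n₁ + 1/n₂)). The losses in the lower three rows are assumptions.

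| Completers in the two arms compared | Noncentrality | Power |
|---|---|---|
| 60 and 60 (the plan: at least 80%) | 2.848 | 80.6% |
| 60 and 59 | 2.836 | 80.3% |
| 59 and 59 | 2.824 | 80.0% |
| 58 and 58 | 2.800 | 79.3% |

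**The case against.** The strongest reply is that the mismatch is real but the section as a whole already handles the event. Section 9.3 lets the investigator withdraw anyone at any time for safety. It also lists a serious or intolerable adverse event and any medically appropriate reason, under the same stem as the C-SSRS entry. An attempt that threatens life, leads to admission or counts as an important medical event is serious under Section 12.2.1. Section 12.3.9 requires immediate contact with the sponsor over urgent hazards. Items 4 and 5 act before any behavior occurs. FDA may have asked for exactly this trigger, in which case only the word behavior is wrong.

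Much of this stands as a limit on size. Actual attempts are the best-covered events; what is left is mostly aborted or interrupted attempts and preparatory acts. The denied-intent route is the weaker of the two, since a rater who infers intent for an attempt might also mark ideation. The form leaves both determinations to the rater's judgment. The skip pattern is the clear case.

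It does not remove the point. The other routes turn on how an event is classified or on investigator opinion. Section 12.1 says worsening of the disease under study is not reported as an adverse event, which leaves room for a site to attribute suicidality to the schizophrenia. Section 4.1 does list suicidal thoughts among adverse events, but in an earlier D-serine study. Section 12.3.9 is a duty to make contact, not a withdrawal criterion. The FDA request is not in the documents, so it is a reason to check before amending and does not justify the present text.

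**Conclusion.** The concern holds. As written, the suicidality criterion in Section 9.3 can be unmet when suicidal behavior has been recorded on the C-SSRS. This follows from the form and its skip pattern and needs no assumption about rates.

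How often it would happen cannot be derived from the documents. It is probably rare: Exclusion 10 removes patients with suicidal behavior in the past year, and most patients with such behavior would be expected to answer yes to item 4 or 5. That last expectation is a judgment, not a figure from the plan. The event is uncommon but potentially grave, and the correction is nearly free, so the wording should be changed. The corrected rule would still depend on rater judgment; the gain is that it would name the event it is meant to catch.

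**What to change.** Replace the entry in Section 9.3 with:

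> Have any suicidal behavior recorded on the C-SSRS (actual, interrupted or aborted attempt, or preparatory acts), or a yes on suicidal ideation item 4 or 5.

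Sites can apply the first part from the summary yes/no question that closes the behavior block of the form. Exclusion 10 already treats past-year behavior and items 4 or 5 as separate grounds, although it does not cite the C-SSRS behavior block. Check the new text against the FDA request before amending.

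The cost is a one-sentence amendment and a memo to sites, with no added assessment. A few more patients might be withdrawn. On the assumed losses above, power would move from 80.6% to between 80.3% and 79.3%. That probably overstates the cost, because withdrawn patients with at least one post-baseline PANSS stay in the Efficacy Population and contribute to the repeated-measures model (SAP Sections 5.1.2.2 and 5.4.1).

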9.3.1. Patient Withdrawal Procedures

A patient who prematurely discontinues Study Medication/study participation should have all Week 12 assessments performed as an Early Termination Visit, and if possible, return for the Safety Follow-up Visit. In light of the COVID-19 pandemic, study personnel should strive to perform assessments per [Table 6](#) with the understanding that not all assessments may be able to be performed. All missed assessments will be documented in the eCRF with notation that the missed assessment was due to the COVID-19 pandemic. The Safety Follow-Up Visit may be waived by the Sponsor in instances where patients have discontinued dosing prior to the Early Termination Visit on a case-by-case basis.

If a patient terminates early from the study, the Investigator will record the reason(s) for early termination on the relevant electronic case report form (eCRF). The specific reason for the withdrawal should be carefully documented on the eCRF.

Adverse events resulting in patient early termination will be followed to the satisfactory resolution and determination of outcome, as ascertained by the Investigator (and/or Sponsor, or its designee); (See Section 12). The data will be recorded on the appropriate eCRF.

10. DESCRIPTION OF STUDY MEDICATIONS

10.1. Description of Study Medication

Patients meeting eligibility criteria will be randomized in a 1:1:1:1 ratio to one of the following 4 treatment arms:

- Double-blinded CTP-692, 1 g QD for 12 weeks
- Double-blinded CTP-692, 2 g QD for 12 weeks
- Double-blinded CTP-692, 4 g QD for 12 weeks
- Double-blinded Placebo, QD for 12 weeks

Patients will take the first dose of Study Medication in the clinic on Day 1 of the Treatment Period, after the Baseline assessments have been performed and with food. Patients will be instructed to continue taking their Study Medication once daily with food, for a total of 12 weeks. On clinic visit days, when patients take their dose of Study Medication in the clinic, the dose should be administered after the clinical laboratory blood draws and urine collection are completed. If clinical laboratory blood draws and urine collection are performed by a Home Health Care service provider or by a local laboratory, patients should try to take their Study Medication per their normal schedule.

10.2. Treatment Compliance

At each scheduled study visit after randomization, the Investigator or designee will interview the patient regarding treatment compliance and compare the number of dispensed versus returned Study Medication pouches. When study assessments are not conducted in the clinic due to the COVID-19 pandemic, treatment compliance may be assessed via phone/audio or video conferencing platforms or by the Home Health Care service provider. The used and unused Study Medication pouches may be sent back to the site or the patient may save the used and unused pouches and bring back to the next in-clinic visit. Patients should strive for 100% compliance with the daily dosing schedule. Retraining on treatment compliance should occur for patients with less than 80% compliance at any visit and the Sponsor should be notified.

10.3. Study Medication Materials and Management

A complete description of the Study Medication and requirements for storage, handling, dispensing, accountability, returns and destruction can be found in the Pharmacy Manual.

10.3.1. Physical Description of Study Medication

Study Medication will be CTP-692 or matching Placebo. Details regarding formulation and dosage are shown in [Table 7](#).

Table 7: Investigational Product

	Investigational Product
Product Name:	CTP-692 or Matching Placebo
Dosage Form:	Powder for oral solution
Unit Dose	1 g, 2 g or 4 g CTP-692 or Placebo
Route of Administration	Oral
Physical Description	White to off-white powder in a foil pouch
Manufacturer	Sharp Clinical Services, Inc.

10.3.2. Study Medication Packaging, Labelling and Storage

CTP-692 and Placebo will be packaged in foil pouches and labeled by an appropriately qualified vendor. Starting at Day 1 and at each scheduled in-clinic visit, each patient will receive 2 kits containing doses for 2 weeks. When study assessments are not conducted in the clinic due to the COVID-19 pandemic, the Study Medication will be sent directly to the patient.

Details of the packaging, labeling and dispensing instructions can be found in the Pharmacy Manual.

Study Medication should be stored at the clinic in the original package between 15°C to 25°C (59°F to 77°F), as stated on the product label, in a secure, temperature-monitored, locked area, under the responsibility of the Investigator or other authorized individual until dispensed to the patients.

Patients should be advised to store their Study Medication in the original package at room temperature as stated on the package label. No special handling procedures are required.

10.3.3. Study Medication Preparation and Administration

Study Medication will be supplied to patients as powder in a foil pouch. Patients will open the pouch by hand using a fold-over tear notch or by using scissors to cut across the top of the pouch. The dose solution should be prepared daily by dissolving the entire contents of a single pouch in approximately a half-glass or half-cup of water and mixing with a spoon for approximately 30 seconds until dissolved. Upon completion of preparation, the dose solution is colorless and slightly hazy in appearance. The dose solution should be consumed immediately.

Patients will take the first dose of Study Medication in the clinic on Day 1 and will be instructed to continue taking Study Medication once daily with food, for a total of 12 weeks. Patients should be instructed to take Study Medication at approximately the same time each day. If a dose is missed, the patient should resume dosing as soon as possible. The patient should not take

two doses at the same time. Deviations from prescribed dosing should be discussed at each visit for assessment of compliance and retraining when necessary.

10.3.4. Study Medication Return and Disposal

The Sponsor or designee will review with the Investigator and relevant site personnel the process for Study Medication return, disposal, and/or destruction, including responsibilities for the site versus the Sponsor (or designee). Specific requirements for destruction or return can be found in the Pharmacy Manual.

10.3.5. Study Medication Accountability

To satisfy regulatory requirements regarding drug accountability, all Study Medication will be reconciled in full. The Investigator or designee must maintain accurate records of the receipt of Study Medication, including date received, lot number, amount received, condition of the package, and the disposition of Study Medication.

Current dispensing records will also be maintained, including the date and amount of medication dispensed to each individual patient. Returned Study Medication records will be maintained and final Study Medication reconciliation will also be recorded for each patient.

